## 11.0 ADVERSE EVENT REPORTING REQUIREMENTS

### 11.1 Purpose

Adverse event data collection and reporting, which are required as part of every clinical trial, are done to ensure the safety of patients enrolled in the studies as well as those who will enroll in future studies using similar agents. Certain adverse events must be reported in an expedited manner to allow for timelier monitoring of patient safety and care. The following sections provide information about expedited reporting.

### 11.2 Determination of Reporting Requirements

Reporting requirements may include the following considerations: 1) whether the patient has received an investigational or commercial agent; 2) the characteristics of the adverse event including the *grade* (severity), the *relationship to the study therapy* (attribution), and the *prior experience* (expectedness) of the adverse event; 3) the Phase (1, 2, or 3) of the trial; and 4) whether or not hospitalization or prolongation of hospitalization was associated with the event.

An investigational agent is a protocol drug administered under an Investigational New Drug Application (IND). In some instances, the investigational agent may be available commercially, but is actually being tested for indications not included in the approved package label.

Commercial agents are those agents not provided under an IND but obtained instead from a commercial source. The NCI rather than a commercial distributor may on some occasions distribute commercial agents for a trial.

When a study includes both investigational and commercial agents, the following rules apply:

- *Concurrent administration*: When an investigational agent is used in combination with a commercial agent, the combination is considered to be investigational and expedited reporting of adverse events would follow the guidelines for investigational agents.
- *Sequential administration*: When a study includes an investigational agent and a commercial agent on the same study arm, but the commercial agent is given for a period of time prior to starting the investigational agent, expedited reporting of adverse events which occur prior to starting the investigational agent would follow the guidelines for commercial agents. Once therapy with the investigational agent is initiated, all expedited reporting of adverse events follow the investigational agent reporting guidelines.

### 11.3 Steps to Determine if an Adverse Event is to be Reported in an Expedited Manner

#### Step 1: Identify the type of event using the NCI Common Terminology Criteria

The descriptions and grading scales found in the revised NCI Common Terminology Criteria for Adverse Events (CTCAE) version 5.0 will be utilized for AE reporting. All appropriate treatment areas should have access to a copy of the CTCAE version 5.0. A copy of the CTCAE version 5.0 can be downloaded from the CTEP web site

[http://ctep.cancer.gov/protocolDevelopment/electronic\\_applications/ctc.htm](http://ctep.cancer.gov/protocolDevelopment/electronic_applications/ctc.htm).

#### Step 2: Grade the event using the NCI CTCAE.

Step 3: Determine the attribution of adverse event in relation to the protocol therapy. Attribution categories are: Unrelated, Unlikely, Possible, Probable, and Definite.

#### Step 4: Determine the prior experience of the adverse event

Expected events for a CTEP IND agent are defined as those listed in the SPEER (Specific Protocol Exceptions to Expedited Reporting), a subset of the CAEPR (Comprehensive Adverse Event and Potential Risks). For investigational agents that are not commercially available and are being studied under a company's IND, expected AEs are usually based on the Investigator's Brochure.

**Unexpected events for a CTEP IND agent are defined as those NOT listed in the SPEER.**

Guidance on expectedness of the agent is provided in the [Drug Information Section](#) of this protocol.

Step 5: Review Tables A and/or B in this section to determine if:

- there are any protocol-specific requirements for expedited reporting of specific adverse events that require special monitoring; and/or
- there are any protocol-specific exceptions to the reporting requirements.

Step 6: Determine if the protocol treatment given prior to the adverse event included an investigational agent, a commercial agent, or a combination of investigational and commercial agents.

**Note:** If the patient received at least one dose of investigational agent, follow the guidelines in Table A. If no investigational agent was administered, follow the guidelines in Table B.

#### 11.4 Reporting Methods

- Use the NCI's CTEP Adverse Event Reporting System (CTEP-AERS). The NCI's guidelines for CTEP-AERS can be found at:

[http://ctep.cancer.gov/protocolDevelopment/electronic\\_applications/adverse\\_events.htm](http://ctep.cancer.gov/protocolDevelopment/electronic_applications/adverse_events.htm)

An CTEP-AERS report must be submitted by the following method: <https://eapps-ctep.nci.nih.gov/ctepaers>

Electronically submit the report via the CTEP-AERS Web-based application located at

- Fax supporting documentation **for AEs related to investigational agents** to:
  - The NCI for agents supplied under a CTEP IND **only** ([contact]).
  - **and** to COG for **all** studies ([contact]; email: [[contact]](mailto:[contact]); Attention: COG CTEP-AERS Coordinator).
- **DO NOT send the supporting documentation for AEs related to commercial agents to the NCI.** Fax or email this material to COG ([contact]; email: [[contact]](mailto:[contact]); Attention: COG AERS Coordinator).

**ALWAYS include the ticket number on all faxed documents.**

- **Use the NCI protocol number and the protocol-specific patient ID provided during trial registration on all reports.**

#### 11.5 When to Report An Event In An Expedited Manner

- Some adverse events require notification **within 24 hours** (refer to Table A) to NCI via the web based application **and/or by telephone call to the Study Chair.**

In the rare situation where Internet connectivity is disrupted, the 24-hour notification is to be made to the NCI for agents supplied under a CTEP IND by telephone call to [contact].

In addition, once Internet connectivity is restored, a 24-hour notification that was phoned in must be entered into the electronic CTEP-AERS system by the original submitter of the report at the site.

- Submit the report **within 5 calendar days** of learning of the event.

#### 11.6 **Other Recipients of Adverse Event Reports**

COG will forward reports and supporting documentation to the Study Chair, to the FDA (when COG holds the IND) and to the pharmaceutical company (for industry sponsored trials).

Adverse events determined to be reportable must also be reported according to the local policy and procedures to the Institutional Review Board responsible for oversight of the patient.

#### 11.7 **Reporting of Adverse Events For Investigational Agents – CTEP-AERS 24-hour Notifications, and Complete Report Requirements.**

Reporting requirements are provided in Table A. The investigational agent used in this study is Temsirolimus.

Table A

**Phase 2 and 3 Trials and COG Group-wide Pilot Studies utilizing an Agent under a CTEP IND or a Non-CTEP IND: CTEP-AERS Expedited Reporting Requirements for Adverse Events That Occur Within 30 Days of the Last Dose of the Investigational Agent**

FDA REPORTING REQUIREMENTS FOR SERIOUS ADVERSE EVENTS (21 CFR Part 312)  NOTE: Investigators MUST immediately report to the sponsor (NCI) ANY Serious Adverse Events, whether or not they are considered related to the investigational agent(s)/intervention (21 CFR 312.64)  An adverse event is considered serious if it results in ANY of the following outcomes:  1) Death.  2) A life-threatening adverse event.  3) Any AE that results in inpatient hospitalization or prolongation of existing hospitalization for <math>\geq 24</math> hours. This does not include hospitalizations which are part of routine medical practice.  4) A persistent or significant incapacity or substantial disruption of the ability to conduct normal life functions.  5) A congenital anomaly/birth defect.  6) Important Medical Events (IME) that may not result in death, be life threatening, or require hospitalization may be considered serious when, based upon medical judgment, they may jeopardize the patient or subject and may require medical or surgical intervention to prevent one of the outcomes listed in this definition. (FDA, 21 CFR 312.32; ICH E2A and ICH E6.)
				

ALL SERIOUS adverse events that meet the above criteria MUST be immediately reported to the NCI via CTEP-AERS within the timeframes detailed in the table below.
				
Hospitalization	Grade 1 Timeframes	Grade 2 Timeframes	Grade 3 Timeframes	Grade 4 & 5 Timeframes
Resulting in Hospitalization <math>\geq 24</math> hrs	7 Calendar Days			24-Hour Notification 5 Calendar Days
Not resulting in Hospitalization <math>\geq 24</math> hrs	Not Required		7 Calendar Days	

NOTE: Protocol specific exceptions to expedited reporting of serious adverse events are found in the Specific Protocol Exceptions to Expedited Reporting (SPEER) portion of the CAEPR. Additional Special Situations as Exceptions to Expedited Reporting are listed below.
 
Expedited AE reporting timelines are defined as:  “24-Hour; 5 Calendar Days” - The AE must initially be reported via CTEP-AERS within 24 hours of learning of the AE, followed by a complete expedited report within 5 calendar days of the initial 24-hour notification.  “7 Calendar Days” - A complete expedited report on the AE must be submitted within 7 calendar days of learning of the AE.
				

SAEs that occur more than 30 days after the last administration of investigational agent/intervention and have an attribution of possible, probable, or definite require reporting as follows:  Expedited 24-hour notification followed by complete report within 5 calendar days for:
 
 
All Grade 4, and Grade 5 AEs
 
 
Expedited 7 calendar day reports for:
 
 
Grade 2 adverse events resulting in hospitalization or prolongation of hospitalization
 
Grade 3 adverse events
 
				

Note: **All deaths on study require timely reporting to COG via RDE regardless of causality. Attribution to treatment or other cause must be provided.**

- **Expedited AE reporting timelines defined:**
  - “24 hours; 5 calendar days” – The investigator must initially report the AE (via CTEP-AERS for CTEP IND agents; via e-mail to COG AE Coordinator for agents in non-CTEP IND studies) within 24 hours of learning of the event followed by a complete CTEP-AERS report within 5 calendar days of the initial 24-hour report.
  - “5 calendar days” - A complete CTEP-AERS report on the AE must be submitted within 5 calendar days of the investigator learning of the event.
- Any medical event equivalent to CTCAE Grade 3, 4, or 5 that precipitates hospitalization (or prolongation of existing hospitalization) must be reported regardless of attribution and designation as expected or unexpected with the exception of any events identified as protocol-specific expedited adverse event reporting exclusions.
- Any event that results in persistent or significant disabilities/incapacities, congenital anomalies, or birth defects must be reported via CTEP-AERS if the event occurs following treatment with an agent under a CTEP IND.
- Use the NCI protocol number and the protocol-specific patient ID provided during trial registration on all reports.
- Protocol specific reporting of AEs, in addition to the CTEP-AERS requirements, are to be entered in the COG remote data entry system.

**Additional Instructions or Exceptions to CTEP-AERS Expedited Reporting Requirements for Phase 2 and 3 Trials Utilizing an Agent under a CTEP IND or Non-CTEP IND:**

- **Any death that occurs more than 30 days after the last dose of treatment with an investigational agent which can be attributed (possibly, probably, or definitely) to the agent and is not due to cancer recurrence/progression must be reported via CTEP-AERS for an agent under a CTEP IND [and via CTEP-AERS for non-CTEP IND agent] per the timelines outlined in the table above.**

**Grades 1- 4 myelosuppression do not require expedited reporting unless unexpected.**

- As of August 25, 2010 all secondary malignancies should be reported via CTEP-AERS.

**11.8 Reporting of Adverse Events for commercial agents – CTEP-AERS abbreviated pathway**

The following are expedited reporting requirements for adverse events experienced by patients on study who have not received any doses of an investigational agent on this study. Commercial reporting requirements are provided in Table B.

COG requires the CTEP-AERS report to be submitted **within 5 calendar days** of learning of the event.

**Table B**

**Reporting requirements for adverse events experienced by patients on study who have NOT received any doses of an investigational agent on this study.**

**CTEP-AERS Reporting Requirements for Adverse Events That Occur During Therapy With a Commercial Agent or Within 30 Days**

Attribution	Grade 4		Grade 5
	Unexpected	Expected	
Unrelated or Unlikely			CTEP-AERS
Possible, Probable, Definite	CTEP-AERS		CTEP-AERS
 This includes all deaths within 30 days of the last dose of treatment with a commercial agent, regardless of attribution. Any death that occurs more than 30 days after the last dose of treatment with a commercial agent which can be attributed (possibly, probably, or definitely) to the agent and is not due to cancer recurrence must be reported via CTEP-AERS.			

As of August 25, 2010 all secondary malignancies should be reported via CTEP-AERS.

**11.9 Routine Adverse Event Reporting**

**Note:** The guidelines below are for routine reporting of study specific adverse events on the COG case report forms and do not affect the requirements for CTEP-AERS reporting.

The NCI defines both routine and expedited AE reporting. Routine reporting is accomplished via the Adverse Event (AE) Case Report Form (CRF) within the study database. For this study, routine reporting will include non-hematological adverse events of Grade 3 or higher (any attribution), as well as any toxicity that required submission of an CTEP-AERS report as outlined above in Sections 11.7, [Table A](#) and 11.8, [Table B](#).

**12.0 RECORDS AND REPORTING**

**12.1 Categories of Research Records**

Research records for this study can be divided into 3 categories:

Non-computerized information: Pathology Narrative Reports and Surgical Reports. These forms are submitted through the Document Imaging System in eRDES.

1. Reference Labs' required reports and IROC RI (QARC) data. These data accompany submissions to these centers which forward their review data electronically to the COG Statistics and Data Center.
2. Computerized Information Electronically Submitted: All other computerized data will be entered in the COG Remote Data Entry System with the aid of schedules and Case Report Forms (paper copies of the RDE screens) provided in the data form packet. The packet is posted on the COG Website with each protocol under "*Data Collection/Specimens*".

**12.2 CDUS**

This study will be monitored by the Clinical Data Update System (CDUS). Cumulative CDUS data will be submitted quarterly to CTEP by electronic means. Reports are due January 31, April 30, July 31 and October 31. This is not a responsibility of institutions participating in this trial.

**13.0 SURGICAL GUIDELINES**

Timing of protocol therapy administration, response assessment studies, and surgical interventions are based on schedules derived from the experimental design or on established standards of care. Minor unavoidable departures (up to 72 hours) from protocol directed therapy and/or disease evaluations (and

---

up to 1 week for surgery) for valid clinical, patient and family logistical, or facility, procedure and/or anesthesia scheduling issues are acceptable per COG Administrative Policy 5.14 (except where explicitly prohibited within the protocol).

### 13.1 Surgical Resection Guidelines

Surgical resection guidelines will be determined according to the PRETEXT grouping system, which was designed specifically for patients with liver tumors. See [Section 10.2](#) and [Appendix I](#) for PRETEXT guidelines. Terminology for PRETEXT grouping at diagnosis is “PRETEXT”. PRETEXT assignment AFTER chemotherapy is referred to as “POST-TEXT”. Please refer to [Appendix I](#) for diagram of resection guidelines.

#### 13.1.1a Tumors Considered Resectable at Diagnosis

##### Non-Extreme Resection

- PRETEXT 1.
- PRETEXT 2 with >1 cm radiographic margin on the middle hepatic vein, the retrohepatic IVC and the portal bifurcation.

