
Specific guidelines for surgical approaches to hepatoblastoma are provided in AHEP0731 since surgery is the critical component necessary for obtaining a cure. Patients with PRETEXT 1 and 2 tumors that have a clear radiographic 1 cm margin on CT or MRI imaging at diagnosis should have a resection performed as soon as possible after the diagnosis of hepatoblastoma is confirmed. The surgical strategy for patients with more advanced PRETEXT-group disease is described in the surgical guidelines section of the protocol (see [Section 13.0](#)).

No patient with Stage IV disease will be offered a liver transplant unless all metastatic extra-hepatic disease has been radiographically documented to either have disappeared as a result of neoadjuvant chemotherapy or has been surgically removed.

The historical barrier of “unresectability” can be redefined with the concept of “total liver resection” and salvage OLT. Interestingly, although 1 of the first long-term survivors of liver transplantation was a child with hepatoblastoma, the role of liver transplantation in the treatment of pediatric hepatoblastoma has never been fully defined. Because liver transplant has not historically been offered to these children as part of a planned treatment algorithm, the optimal timing of transplantation and the potential role of post transplant adjuvant chemotherapy remain unclear. Largely due to negative experience with liver transplant in the treatment of adult hepatocellular carcinoma, liver transplant for the treatment of hepatic malignancy developed an early reputation as a dreaded, heroic last resort, and even potentially ethically-inappropriate intervention. But the biology of pediatric hepatoblastoma has proven to be very different from that of adult hepatocellular carcinoma, and experience with liver transplantation for hepatoblastoma has been far more favorable.

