#### 13.1.1b Tumor Biopsy Only at Diagnosis (Stage III)

- PRETEXT 2 with *less than* 1 cm radiographic margin on the middle hepatic vein, the retrohepatic IVC, and the portal bifurcation.
- PRETEXT 3.
- PRETEXT 4.
- Biopsy technique at the discretion of the treating institution may be a percutaneous tru-cut, laparoscopic tru-cut or wedge, or open biopsy. Minimum biopsy size is 3 tru-cut cores of tissue. Larger biopsies, however, are strongly recommended where feasible to evaluate for the possibility of heterogenous foci of small-cell undifferentiated (SCU) tumor. (See [Section 14.0](#) for Pathology specimen requirements.)

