#### 13.1.2 Tumors Considered Resectable After First 2 Cycles of C5VD Neoadjuvant Chemotherapy

##### Non-Extreme Resection

See [Section 14.0](#) for Pathology specimen requirements.

- Tumors with POST-TEXT 1.
- Tumor with POST-TEXT 2 with > 1 cm radiographic margin on the middle hepatic vein, the retrohepatic IVC, or the portal bifurcation.

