#### 13.1.4 Tumors Considered Resectable Within 4 weeks of Completing 4th Cycle of Chemotherapy Non-Extreme Resection

See [Section 14.0](#) for Pathology specimen requirements.

- Tumors with POST-TEXT 3 and no major venous invasion. The surgeon must anticipate the ability to achieve a negative surgical margin on the right/left hepatic vein, retrohepatic IVC, or portal bifurcation. Margin may be less than 1 cm if the surgeon feels a complete resection will be feasible without transplant and patient has completed 4 cycles of C5VD chemotherapy.

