#### 13.1.5 Tumors Presenting with Metastatic Disease (Stage IV)

See [Section 14.0](#) for Pathology specimen requirements.

- Complete 2 cycles of upfront experimental window chemotherapy.
- Repeat radiographic imaging after completing upfront window therapy
  - Resect (non-extreme) tumors POST-TEXT 1 or 2 with > 1 cm radiographic margin on the middle hepatic vein, retrohepatic IVC, and portal bifurcation
  - For all others, proceed with 2 cycles of C5VD
- Repeat radiographic imaging after completing first 2 cycles of C5VD
  - Resect (non-extreme) tumors downstaged to POST-TEXT Group 1, 2, or 3 tumors with > 1 cm radiographic margin on right/left hepatic vein, retrohepatic IVC, and portal bifurcation.
  - For patients potentially needing liver transplant/extreme resection (see definition in [Section 13.1.3](#)), refer to surgical center with expertise in pediatric liver transplant and “extreme” liver resection at diagnosis if possible and no later than the FIRST DAY of the 3rd cycle of C5VD chemotherapy. Resection planning is to be completed before completion of Cycle 7 in high risk responders and before completion of Cycle 6 in high risk non-responders. Transplant or “extreme” resection is to occur within 4 weeks of completing the 7th cycle of chemotherapy in high risk responders and the 6th cycle of chemotherapy in high-risk non-responders.
  - Repeat chest CT scan must demonstrate complete clearance of pulmonary metastatic disease within 1 week prior to liver transplant.
  - Those patients with persistent extrahepatic disease, may be resected (not transplanted) at the discretion of the surgical center with expertise in pediatric liver transplant and “extreme” liver resection.
  - Those patients with persistent extrahepatic disease who are not anatomically resectable without transplantation will continue chemotherapy.

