## Resect at Diagnosis

Easy lobectomy with > 1 cm margin:

- PRETEXT 1
- PRETEXT 2

Diagnosis CT shows unifocal tumor with at least 1cm clear radiographic margin from middle hepatic vein and portal bifurcation

[figure not shown]
AHEP 0731 Surgical Resection Guidelines

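### Group 2 resection criteria are worded inconsistently: Section 13.1.2 prints 'or' where 'and' is meant, the Appendix I text does not name the IVC, and 13.1.1b is not the complement of 13.1.1a

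*Combined protocol and SAP*

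**What the plan says.** **At diagnosis**

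- Section 13.1.1a allows resection of "PRETEXT 2 with >1 cm radiographic margin on the middle hepatic vein, the retrohepatic IVC and the portal bifurcation".
- Section 13.1.1b sends PRETEXT 2 to biopsy only when there is less than "1 cm radiographic margin on the middle hepatic vein, the retrohepatic IVC, and the portal bifurcation".
- Appendix I has a resect-at-diagnosis page headed "Easy lobectomy with > 1 cm margin". Its detailed line reads "Diagnosis CT shows unifocal tumor with at least 1cm clear radiographic margin from middle hepatic vein and portal bifurcation".
- Section 2.5 recommends early resection of "PRETEXT 1 and 2 tumors that have a clear radiographic 1 cm margin on CT or MRI imaging at diagnosis", without listing structures.

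**After chemotherapy**

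- Section 13.1.2, after the first two C5VD cycles: "Tumor with POST-TEXT 2 with > 1 cm radiographic margin on the middle hepatic vein, the retrohepatic IVC, or the portal bifurcation".
- Appendix I, after the second cycle: POST-TEXT 2 is resected if the margin exceeds 1 cm on the middle hepatic vein *and* the portal bifurcation. POST-TEXT 2 with a margin under 1 cm is held until after the fourth cycle.
- Section 13.1.4, after four cycles, concerns POST-TEXT 3. It asks for a "negative surgical margin on the right/left hepatic vein, retrohepatic IVC, or portal bifurcation" and allows less than 1 cm if complete resection is judged feasible.
- Section 13.1.5, Stage IV after window therapy: "tumors POST-TEXT 1 or 2 with > 1 cm radiographic margin on the middle hepatic vein, retrohepatic IVC, and portal bifurcation". After two C5VD cycles it has a separate rule based on the right/left hepatic vein.

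Section 13.1 refers the reader to Appendix I for the diagram of these guidelines. I found no statement of which text prevails if they differ.

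**The concern.** These lines are operative surgical instructions. Section 2.5 expects the guidelines to steer suitable PRETEXT 1 and 2 tumors to resection at diagnosis, and Section 4.2.1 uses PRETEXT grouping to guide which tumors count as unresectable at diagnosis.

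At diagnosis, the choice of operation fixes the COG stage. Take a child with AFP above 100 ng/mL and non-PFH, non-SCU histology. Resection leads to Stage I or II and 2 cycles of C5V, with cisplatin 2 × 100 = 200 mg/m² and no doxorubicin. Biopsy leads to Stage III and 6 cycles of C5VD, with cisplatin 6 × 100 = 600 mg/m² and doxorubicin 6 × 2 × 30 = 360 mg/m². The biopsy route was open only until Stratum 3 closed on 03/12/12.

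After two C5VD cycles, the stake is timing. A literal *or* would send a tumor lying against the portal bifurcation to surgery earlier than Appendix I does, which bears on surgical safety.

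**Working it through.** The plan gives no figure to reproduce, so the check sets the criteria side by side and runs test tumors through them. Write V for the middle hepatic vein, C for the retrohepatic IVC and P for the portal bifurcation.

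| Text | Timepoint | Threshold | Structures | Joined by |
|---|---|---|---|---|
| 13.1.1a | diagnosis, resect | > 1 cm | V, C, P | and |
| 13.1.1b | diagnosis, biopsy | < 1 cm | V, C, P | and |
| App. I heading | diagnosis, resect | > 1 cm | none named | – |
| App. I detailed line | diagnosis, resect | ≥ 1 cm | V, P | and |
| 13.1.2 | after 2 C5VD cycles, resect | > 1 cm | V, C, P | **or** |
| App. I | after cycle 2, resect | > 1 cm | V, P | and |
| App. I | after cycle 4, resect | < 1 cm | none named | – |
| 13.1.5 | Stage IV after window, resect | > 1 cm | V, C, P | and |

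**Tumor A: POST-TEXT 2 after two C5VD cycles, close to P only.** Under the literal 13.1.2 it is clear of V and C, so *or* is satisfied and it is resected now. Under Appendix I it fails on P and waits until after cycle 4. The gap is 2 cycles × 21 days = 42 days. On Regimen F the total stays at 6 cycles, split 2 + 4 or 4 + 2 around surgery.

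Three features mark the *or* as a slip:

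- Appendix I at the same timepoint uses *and*, and gives close-margin POST-TEXT 2 its own later slot.
- Section 13.1.5 uses *and* over the same three structures. It is a weaker comparator because it applies to Stage IV after window therapy.
- Section 13.1.4 uses a similar loose *or* where only *each of* makes sense.

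**Tumor B: PRETEXT 2 at diagnosis, close to C only.** Under 13.1.1a it is not resected. Under the Appendix I detailed line alone it is. If the Appendix I heading covers every structure, it is not. Of the 2³ = 8 close/clear patterns over V, C and P, the two texts therefore differ in 1 (this one) or in 0. Once the *or* in 13.1.2 is read as *and*, the same single IVC pattern is all that separates it from the Appendix I cycle-2 line.

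**Tumor C: PRETEXT 2 at diagnosis, close to V only.** It fails 13.1.1a. Read literally it also misses 13.1.1b, which asks for a short margin on all three. Read in the ordinary way, 13.1.1b is the biopsy counterpart of 13.1.1a and the tumor is biopsied.

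**Tumor D: exactly 1 cm on P, more on V and C.** At diagnosis it fails 13.1.1a (> 1 cm) and misses 13.1.1b (< 1 cm). It passes the Appendix I detailed line and fails the Appendix I heading. After cycle 2 it fits neither the cycle-2 nor the cycle-4 line of Appendix I.

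**Check of the proposed wording.** Give each structure three levels (< 1, = 1, > 1 cm), so 3³ = 27 patterns.

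- Resect after cycle 2 if > 1 cm on all three: 1 pattern.
- Resect after cycle 4 if 1 cm or less on any of the three: 27 − 1 = 26 patterns.
- Together 1 + 26 = 27, with none unassigned and none assigned twice. The same holds for 13.1.1a paired with the reworded 13.1.1b.
- If the cycle-4 line kept a strict < 1 cm on any structure, the patterns with no margin below 1 cm number 2³ = 8. One of these is taken at cycle 2, so 8 − 1 = 7 would have no slot.

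These are counts of logical patterns, not of patients. The documents give no distribution of margins.

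**The case against.** The strongest reply is that this is copy-editing. Section 13.1.6 leaves resectability to the local institution, with a study surgeon available on request, and Section 4.5 allows removal after two cycles if judged feasible. Stage I and II children are operated on before enrollment, because enrollment waits for rapid pathology review, and no eligibility criterion requires compliance with 13.1.1a. Section 13.1 presents Appendix I as an illustration, and its figures are missing from the copy reviewed. The figures may show the IVC, and the Appendix I heading may already cover it. A competent surgeon would read 13.1.1b as the counterpart of 13.1.1a and 13.1.2 as *each of*.

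Most of this stands. It removes any claim of demonstrated harm and leaves the IVC point conditional. It also disposes of a stronger reading that a reader might infer: that literal wording leaves most margin patterns unassigned at diagnosis, or puts 13.1.2 and Appendix I in conflict over most of them. Those literal counts vanish on the ordinary reading and should carry no weight. What the reply does not remove is that 13.1.2, as printed, says something different from Appendix I at the same timepoint.

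**Conclusion.** The point holds as a minor internal inconsistency. The *or* in 13.1.2 is wrong as written and almost certainly a drafting error. The Appendix I text omits the IVC in both resect lines and mixes > 1 cm with at least 1 cm at diagnosis. This part is conditional on the heading and the figures not shown. Section 13.1.1b should be worded as the complement of 13.1.1a.

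Two further inferences are tempting but unsupported.

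- **Misclassified children.** Section 4.2.1 excludes PRETEXT grouping from risk classification, and Appendix III stages by the operation performed. No stratum assignment, analysis rule or stated statistical figure depends on this wording. Nothing in the documents shows that an affected tumor was enrolled.
- **One > 1 cm rule at every timepoint.** That would contradict 13.1.4, which permits less than 1 cm after four cycles, the Appendix I cycle-4 line, and the separate right/left hepatic vein rule in 13.1.5.

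The size is confined to surgical selection and timing. The number of children affected cannot be computed. The benefit of correcting it is consistent guidance.

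**What to change.** Limit the change to PRETEXT 2 at diagnosis and POST-TEXT 2 after the second C5VD cycle, with 13.1.1a as the reference text:

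1. Section 13.1.2: change *or* to *and*.
2. Appendix I, resect at diagnosis: name the retrohepatic IVC and use > 1 cm.
3. Appendix I, resect after the second cycle: name the retrohepatic IVC and keep > 1 cm.
4. Section 13.1.1b: reword as *1 cm or less on any of* the three structures.
5. Appendix I, resect after the fourth cycle: reword as *POST-TEXT 2 with 1 cm or less on any of* the three structures.

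Leave 13.1.4 and the right/left hepatic vein rule in 13.1.5 unchanged.

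The cost is five lines of text and no added analysis. Because the study closed on July 20, 2018, the practical step is to state the operative resection rule in the study report, where it also helps in interpreting secondary aim 1.3.5 (whether PRETEXT predicts resectability), and to carry the corrected wording into any successor protocol.
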